1.0 TRIAL SUMMARY

Abbreviated Title	Subcutaneous mosunetuzumab with or without polatuzumab vedotin and obinutuzumab for untreated indolent B-cell non-Hodgkin lymphoma
Trial Phase	Pilot Study
Clinical Indication	Indolent B-cell non-Hodgkin lymphoma (NHL) patients who have not received prior systemic therapy
Trial Type	Nonrandomized, prospective trial
Type of control	N/a
Route of administration	Subcutaneous, IV
Trial Blinding	n/a
Treatment Groups	n/a
Number of trial subjects	42
Estimated duration of trial	30 months (enrollment)
Duration of Participation	38 months

[figure not shown]
2.0 TRIAL DESIGN

Trial Design:

This is a nonrandomized, single-arm pilot study which will evaluate the activity of subcutaneous (SC) mosunetuzumab with or without polatuzumab vedotin and obinutuzumab in untreated indolent B-cell NHL.

Study duration: Subjects will be enrolled over 30 months. Last subject out (completing study follow-up) is projected to occur at around 38 months after study opening. Subsequently, patients may be followed for outcomes for up to 5 years after treatment completion using standard-of-care assessments per local institutional guidelines.

Trial Diagram

Response assessments

Post cycle 4: CT

Post cycle 8: PET/CT

Post cycle 11 (G+P only): CT

Post cycle 14: PET/CT

* Select subjects with PD may proceed through Part A to Part B provided they are deriving clinical benefit from the treatment (e.g. pseudoprogression)

Cycle length: 21 days

Abbreviations: CR: complete remission; CT: computed tomography; G: obinutuzumab; P: polatuzumab vedotin; PET/CT: Positron emission tomography/computed tomography

3.0 OBJECTIVES & HYPOTHESIS

Primary Objective:

Estimate the efficacy of this regimen as measured by the proportion of subjects who have achieved a complete response (CR) as the best response by the end of therapy.

Secondary Objective:

Estimate the end of treatment overall response rate (ORR).

Exploratory Objective:

Estimate the progression-free survival (PFS), and overall survival (OS) for this combination using the appropriate response criteria for the histology tested. Stratify ORR, CR, PFS, DOR (overall and by type of response), and OS by subjects receiving mosunetuzumab alone vs. mosunetuzumab followed by polatuzumab vedotin and obinutuzumab. Estimate the safety of this regimen as measured by the frequency of adverse events (AEs). Correlate clinical outcomes including but not limited to ctDNA analysis, genomics, cytokine levels.

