Promising results led to the initiation of a phase 1b/2 clinical trial of polatuzumab vedotin in combination with R-CHP in DLBCL (R-CHOP with omission of vincristine)⁹. The MTD used in the combination regimen dose expansion cohort was 1.8 mg/kg. A recent update of this study found that the combination was well tolerated, with the most common grade 3-4 toxicities being neutropenia (30%), febrile neutropenia (18%), and thrombocytopenia (9%)⁹. Encouraging results in the dose expansion phase with high international prognostic index (IPI) patients led to the creation of a phase 3 randomized trial that has completed accrual comparing polatuzumab vedotin and R-CHP versus standard R-CHOP chemotherapy without known safety issues from a data safety monitoring committee (NCT03274492). The recommended dose of polatuzumab in this study was 1.8 mg/kg.

Polatuzumab vedotin has been safely combined with obinutuzumab in relapsed/refractory follicular lymphoma with an overall response rate of 78%¹¹. The most common adverse events in > 20% of patients included fatigue (43%), diarrhea (34%), nausea (30%), constipation (21%), and headache (20%).

In addition, polatuzumab vedotin was recently FDA approved in combination with rituximab and bendamustine for patients with DLBCL who have received 2 prior lines of therapy. The recommend polatuzumab vedotin dose to be given every 3 weeks in this regimen is also 1.8 mg/kg.

4.3.2 Rationale for Endpoints:

The primary endpoint is estimating the efficacy of this regimen as measured by the proportion of subjects who have achieved a complete response (CR) as the best response by the end of therapy.

4.3.2.1 Secondary/Exploratory Endpoints:

Secondary endpoint is estimating the end of treatment overall response rate.

Exploratory endpoints include estimating the PFS and OS for this combination using the appropriate response criteria for the histology tested. These also include stratifying ORR, CR, PFS, DOR, and OS by subjects receiving mosunetuzumab alone vs. mosunetuzumab followed by polatuzumab vedotin and obinutuzumab. Additional endpoints include estimating the safety of this regimen as measured by the frequency of adverse events (AEs) and correlating clinical outcomes including but not limited to ctDNA analysis, genomics, cytokine levels.

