Subjects who must permanently discontinue mosunetuzumab monotherapy due to toxicity should have a response assessment with positron emission tomography (PET)/CT as soon as is clinically feasible and be evaluated for consideration of treatment in Part B as outlined below. These subjects would then be realigned to cycle 9 day 1 provided at least 21 days \pm 2 days have passed since the last mosunetuzumab injection

Subjects will undergo a computed tomography (CT) between cycle 4 day 1 and cycle 5 day 1. Those with at least stable disease (SD) or better by Lugano²³ criteria will proceed with treatment for cycles 5-8. Subjects with progressive disease (PD) at this timepoint may proceed with cycles 5-8 if the investigator assesses that the subject is deriving clinical benefit from the study medication (e.g. pseudoprogression). If there is no clinical benefit to this medication seen in patients with PD, subjects should receive additional therapy outside of the protocol.

Imaging with a PET/CT will be performed between cycle 8 day 1 and cycle 9 day 1. Subjects in a complete remission (CR) will not receive any further study therapy and will be observed in long term follow up. For this response assessment, a Deauville score will be assigned by the clinical radiology read. If the sub-investigator or principal investigator disagrees with the Deauville score assigned, another nuclear medicine physician will adjudicate the results.

All other subjects who do not achieve a CR may proceed with Part B of study treatment. Those with progressive disease (PD) may proceed with Part B only if they are deriving clinical benefit from the treatment (e.g., pseudoprogression, mixed response overall reduction in tumor) after discussion with the Principal Investigator.

Mosunetuzumab Dose Modifications/Toxicity Management

Administration of mosunetuzumab will be performed in a clinical setting with immediate access to a code team staff who are trained to monitor for and respond to medical emergencies. Additional management may take place after transfer to the University of Washington Medical Center, where there is access to neurology and nephrology consultation services in the event of cytokine release syndrome and tumor lysis syndrome, respectively.

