The recommended management of CRS is listed in Appendix 14.5 and recommended management of hemophagocytic lymphohistiocytosis (HLH) is listed in Appendix 14.6. Details and recommended management of tumor lysis syndrome are listed in section 14.7 and 14.8.

Because TLS (Appendix 14.7 and 14.8) represents a pharmacodynamic effect of mosunetuzumab anti-tumor activity that may result in clinical benefit, patients who experience Grade 4 TLS may be considered for continued study treatment. In order to be considered for subsequent study treatment, all toxicities and laboratory abnormalities

related to TLS resolved within 2 weeks. The decision to continue study treatment should only be made after consultation with the study investigator and approval by the Principal Investigator. Any exceptions must have the approval of the principal investigator.

Patients who experience a treatment-related grade 3 non-hematologic adverse event or serious adverse event not mentioned above will be allowed to delay mosunetuzumab dosing for up to 2 weeks in order to recover from the toxicity. Additional delays must be discussed with the principal investigator prior to considerations of resuming study therapy.

In general, patients receiving mosunetuzumab who experience a Grade 4 non-hematological treatment-related adverse event should discontinue all study treatment and may not be re-treated. Subjects who discontinue mosunetuzumab due to toxicity may proceed to Part B at investigator discretion, but should have a repeat response assessment prior to initiating therapy in Part B.

For those non-hematologic adverse events that are not considered by the investigator to be attributable to another clearly identifiable cause, (e.g., documented disease progression, concomitant medication, or pre-existing medical condition), and thought to be attributable to mosunetuzumab, patients may continue to receive additional doses of mosunetuzumab, provided that the toxicity has resolved to Grade ≤ 1 . Corticosteroids may be used as indicated for the management of non-CRS adverse events related to mosunetuzumab. One can consider resuming mosunetuzumab after resolution of the toxicity to Grade ≤ 1 and steroid dosing of prednisone ≤ 10 mg PO daily or less

- For decreased lab values, the abnormality should have resolved to the lower limit of Grade ≤ 1 , or return to $\geq 80\%$ of the baseline value, whichever is lower.

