7.1.6.2 Treatment Period

Subjects may be treated in Part A with mosunetuzumab for up to 8 cycles, and for those who do not achieve a CR, in Part B with polatuzumab vedotin and obinutuzumab for up to 6 cycles. Details of pre-medications and schedule of treatments, pre-medications, and assessments have been outlined in sections 5.2 and 6.0.

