Objectives include gaining a preliminary assessment of the potential efficacy of this regimen. This will be defined as the percentage of patients that achieve a complete remission (CR) following study treatment as the primary end point, best ORR as a secondary end point. Exploratory endpoints include with PFS and OS. A simple binary proportion will be used to estimate CR and ORR, and the Kaplan-Meier method will be used to estimate PFS and OS.

Combination chemotherapy with a CD20 monoclonal antibody is highly efficacious in the treatment of indolent lymphomas, but short and long term toxicities can be seen¹⁻³. Since these studies did not all use PET-based assessments, it can be challenging to determine a reasonable

benchmark. However, recent retrospective studies would suggest the CR rate to upfront treatment is around 80%²⁵. Given potential for less toxicity with the proposed treatment, an observed CR rate that is at least as high as this benchmark would be considered promising, pending examination of other endpoints plus toxicity data. Therefore we would consider this study to be successful and merit further investigation if the observed best response as CR rate that is at least 80% among the patients treated. We propose to treat a total of 42 patients, this number not based on considerations of statistical power to reject a null hypothesis, rather on considerations of feasibility and ability to accrue. We anticipate enrolling roughly 42 patients over a 30-month period, but if the protocol is open for 36 months before 42 patients have been enrolled, consideration will be given to closing the study. If we enroll 42 patients, 34 or more complete responses would meet this benchmark. Shown in the table below is the probability of 34 or more responses among 42 patients for a variety of assumed-true CR rates. A subject will be defined as efficacy evaluable if they have had at least one response assessment. Subjects who come off study treatment for any reason prior to a response assessment will not be considered response evaluable and will not be replaced. If fewer than 42 subjects are evaluable for response after completion of the study, we will recalculate the below tables with a goal of achieving a CR as best response in at least 80% of patients.

Assumed-true CR rate	Probability of 34 or more responses among 42 patients
.65	.02
.70	.08
.75	.24
.80	.53
.85	.83
.90	.98

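### The exploratory split by mosunetuzumab alone versus mosunetuzumab then polatuzumab vedotin plus obinutuzumab uses groups set after baseline, so CR in the alone stratum overstates Part A activity and PFS/OS by group cannot be read as a comparison

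*Combined protocol and SAP*

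**What the plan says.** The exploratory objective in section 3.0 stratifies ORR, CR, PFS, DOR and OS "by subjects receiving mosunetuzumab alone vs. mosunetuzumab followed by polatuzumab vedotin and obinutuzumab". Section 4.3.2.1 repeats this among the exploratory endpoints: "These also include stratifying ORR, CR, PFS, DOR, and OS by subjects receiving mosunetuzumab alone".

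Section 5.3 decides who falls in which group. After the PET/CT that follows cycle 8, "Subjects in a complete remission (CR) will not receive any further study therapy and will be observed in long term follow up". Of the rest it says "All other subjects who do not achieve a CR may proceed with Part B of study treatment", and section 7.1.6.2 likewise restricts Part B to subjects not in CR. Three other routes matter:

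- **Progression on the CT after cycle 4.** "If there is no clinical benefit to this medication seen in patients with PD, subjects should receive additional therapy outside of the protocol". These subjects never reach Part B.
- **Toxicity.** "Subjects who discontinue mosunetuzumab due to toxicity may proceed to Part B at investigator discretion". They are realigned to cycle 9 day 1 once about 21 days have passed since the last injection, so they can enter Part B well before week 24.
- **Discretion.** Entry is permitted, not required, and selected subjects with progression may enter if they are judged to benefit.

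On method, section 8.0 says "A simple binary proportion will be used to estimate CR and ORR, and the Kaplan-Meier method will be used to estimate PFS and OS". It does not mention the stratified analysis, and it gives no landmark, no time-dependent treatment and no statement that the split is descriptive.

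**The concern.** The strata are not baseline groups. The alone stratum holds the Part A complete responders plus every non-CR subject who never starts Part B. The Part B stratum holds subjects who were not in CR at the Part A assessment and who stayed on study long enough to enter.

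Two consequences follow if the plan is applied as written. First, CR in the alone stratum depends heavily on how many non-CR subjects are moved out of it, and so says little about how active mosunetuzumab is in Part A. Second, PFS and OS curves drawn from treatment start give the Part B group a period in which its members could not have died, while early deaths and most early progressions fall in the alone group. Selection by response pulls the other way if non-CR carries a worse prognosis.

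In a response-adapted pilot, a later study would want the Part A CR rate over the whole cohort and the conversion rate in Part B. The plan does not name the first. The alone-stratum figure could be quoted in its place.

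**Working it through.** **The plan's own figures.** The only operating-characteristic table is for the primary endpoint in section 8.0. The exact binomial probability of 34 or more CRs in 42, at true rates .65, .70, .75, .80, .85 and .90, is .019, .080, .243, .531, .831 and .979. This agrees with the stated .02, .08, .24, .53, .83 and .98. No figure is given for the split.

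**CR in the alone stratum.** Let pA be the Part A CR rate and q the share of non-CR subjects who never enter Part B. Then

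CR(alone) = pA / [pA + (1 − pA) × q].

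The documents give no Part A CR rate for untreated patients. I take 43% (the relapsed/refractory figure in section 4.3) to 80% (the section 8.0 benchmark) as an assumed range, and q is assumed.

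| True pA | q = 0 | q = 10% | q = 30% |
|---|---|---|---|
| 43% | 100% | 88% | 72% |
| 60% | 100% | 94% | 83% |
| 80% | 100% | 98% | 93% |

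For pA = 60%: 0.60 / (0.60 + 0.40 × 0.10) = 0.60 / 0.64 = 94%, and 0.60 / (0.60 + 0.40 × 0.30) = 0.60 / 0.72 = 83%.

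In whole numbers (assumed): of 42 treated, 25 are in CR after Part A, 5 leave without CR before Part B, 12 enter Part B and 8 of them convert. The split reports 25/30 = 83% and 8/12 = 67%. CR after Part A over all treated is 25/42 = 60%. The Part B figure is already the conversion rate. Its exact 95% interval (Clopper-Pearson) is 35% to 90%.

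**Guarantee time.** 8 cycles × 21 days = 168 days, or 24 weeks (168 / 30.4375 = 5.52 months), for a subject who completes Part A. It is shorter for those realigned early after toxicity.

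**PFS when Part B does nothing.** Assumptions: exponential times, average hazard set to give 80% PFS at 24 months, q = 10%, pA = 60%, and Part B entry at week 24 among event-free non-CR subjects.

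*Response not prognostic.*
- PFS at 5.52 months = 0.8^(5.52/24) = 0.950.
- Part B share = 0.40 × 0.90 × 0.950 = 0.342.
- Part B 24-month PFS = 0.80 / 0.950 = 84%.
- Alone = (0.80 − 0.342 × 0.842) / 0.658 = 78%.
- From a week 24 landmark, 24 months on, both are 80%.

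*Non-CR hazard ratio 3.* The hazards are 1/1.8 and 3/1.8 of the average, since 0.6 × 1 + 0.4 × 3 = 1.8.
- PFS at 24 months is 0.883 for CR and 0.689 for non-CR, or 0.806 overall.
- Non-CR PFS at 5.52 months is 0.918.
- Part B share = 0.36 × 0.918 = 0.3305.
- Part B = 0.689 / 0.918 = 75%.
- Alone = (0.806 − 0.3305 × 0.751) / 0.6695 = 83%.
- From the landmark, 24 months on: 87% versus 69%.

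Over pA of 43% to 80% and hazard ratios of 1 to 3, the 24-month difference (alone minus Part B) runs from about −8 to +14 points with no treatment effect. A simulation on the same assumptions gives the same values to within rounding and sampling error.

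**The case against.** The strongest reply is that the plan claims no comparison. The trial is single-arm, the split is exploratory, and no test or contrast between the groups is specified. As a description of two subsets the figures are valid. That stands, and it limits the point to how the figures would be read and to what is left unreported.

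Several stronger readings are tempting but not supported:

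- **That the split is meant to show what each part adds.** No section states this; it would be an inference.
- **That CR in both groups is fixed in advance.** Part B entrants are generally not in CR at entry, so their CR is essentially the conversion rate: 8/12 in the example, with or without the change. Nor does routing fix ORR, since non-CR subjects occur in both strata.
- **That DOR is shown to be biased.** Section 8.0 gives no method for DOR by group, and the working above does not address it.
- **That response alone forms the groups, with 168 days guaranteed to all of Part B.** Early progression, toxicity and discretion also decide entry, and toxicity discontinuers can enter sooner.

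It is also fair to say that section 8.0 does not define the strata. Subjects who leave before any response assessment are not response evaluable, so some early leavers might not be counted in the alone stratum. That would lower q and move the alone figure closer to 100%. It does not restore the Part A rate.

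**Conclusion.** The point holds in a limited form. Followed as written, CR in the alone stratum overstates Part A activity: a true 60% would read 94% or 83% under the assumed q of 10% or 30%, and 100% if every non-CR subject entered Part B. PFS and OS by group from treatment start combine guarantee time with selection by response. The sign of the resulting bias depends on unknown inputs, as the range of about −8 to +14 points shows. The mechanism follows from the routing rules in section 5.3. The sizes rest on assumed values of pA, q, the PFS rate and the hazard ratio.

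A reader might go on to infer that the trial's main result is compromised. It is not: the primary CR endpoint, the 34-of-42 benchmark and the suspension rules do not use this split. The change is worth making because it is cheap and uses data already collected.

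**What to change.** Add a short paragraph on this split to section 8.0:

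- **(a)** Report CR and ORR at the end of Part A over the whole cohort, with the denominator stated: all treated subjects, and also the response-evaluable set that section 8.0 defines.
- **(b)** Report CR in the Part B stratum explicitly as conversion among entrants not in CR at entry, with an exact confidence interval.
- **(c)** Show PFS and OS by group only from a fixed time after cycle 1 day 1, about week 24 plus a stated window. Classify subjects by status at that time as CR and stopped, Part B entered, or neither, and list earlier events separately. The actual cycle 9 day 1 date is not a common landmark, because toxicity discontinuers reach it early and a drug washout can delay it.
- **(d)** Label the split descriptive and non-comparative.

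The cost is SAP wording and minor programming; the post-cycle 8 scan is already mandatory. There are two downsides. Subjects with events before the landmark drop out of the landmark curves. And the landmark leaves selection by response in place: in the hazard ratio 3 case the gap after it is 87% versus 69% with no Part B effect. The curves must therefore not be read as a treatment comparison.

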4.0 BACKGROUND & RATIONALE

Background

While indolent B-cell non-Hodgkin lymphoma (iNHL) including follicular lymphoma (FL) is not curable with standard therapies, it is highly treatable with chemo-immunotherapy¹⁻³. Retrospective studies have found that up to 80% of FL patients will have overall survival (OS) near age-matched controls, suggesting that many FL patients might have similar outcomes with less intensive therapy^{4,5}. Lenalidomide + rituximab has previously been examined in the upfront setting for 24 months of treatment. While it is “chemo-free,” notable adverse effects include fatigue, cytopenias, and is limited in patients with co-morbidities like chronic kidney disease. Mosunetuzumab, a CD3:CD20 bispecific antibody, and polatuzumab vedotin, an anti-CD79b antibody-drug conjugate, have shown significant activity across multiple B-cell NHL histologies⁶⁻¹⁰. The most recent data of mosunetuzumab monotherapy in relapsed/refractory indolent NHL demonstrated a CR rate of 41%⁶. In addition polatuzumab has been safely combined with obinutuzumab in relapsed/refractory follicular lymphoma with an overall response rate of 78%¹¹.

Obinutuzumab already has an FDA label for treatment-naïve³ and relapsed/refractory¹² follicular lymphoma in combination with chemotherapy. Obinutuzumab has also been used to treat chronic lymphocytic leukemia/small lymphocytic lymphoma in different combinations in the upfront and relapsed refractory settings¹³⁻¹⁵. Obinutuzumab was found to be equivalent to rituximab in aggressive large B-cell lymphomas¹⁵. This makes obinutuzumab an effective partner monoclonal CD20 antibody for treatment of indolent B-cell NHL.

While chemo-immunotherapy is efficacious for untreated iNHL, short-term side effects like fatigue, alopecia, and infections are common, and long-term side effects like secondary malignancies can be seen¹⁶. Given the activity of mosunetuzumab and polatuzumab vedotin in the relapsed/refractory setting, it is reasonable to consider a cytotoxic-chemotherapy-free approach for untreated indolent NHL and expect that CR rates will exceed those seen in the relapsed-setting.

We hypothesize that mosunetuzumab with or without polatuzumab vedotin plus obinutuzumab will produce high complete response rates in indolent non-Hodgkin lymphomas without the need for conventional cytotoxic chemotherapy.

